### Objective:

We are proposing a randomized pilot trial, comparing the effectiveness of one stage to two-stage surgical approach for the creation of an upper arm brachial-basilic arteriovenous fistula (BBAVF). The target population are patients on renal replacement therapy who are receiving hemodialysis (HD) with central venous catheters (CVCs) at the time of the surgery and are candidates for a new BBAVF.

### Design:

A BBAVF is a reliable autogenous hemodialysis access in patients without suitable cephalic vein.[1, 2] It can be created in either one or two stages.[3] The advantage of the one-stage approach is a shorter time between access creation and the cannulation for HD. The disadvantage is the potential for a longer upper arm incision if the AVF fails to mature. Although the two-stage approach can circumvent a more extensive procedure if the AVF fails, the need for two separate operations usually leads to more extended CVC dependency and a higher risk of CVC-related bacteremia (CRB). While literature confirms good results for BBAVFs, comparative studies of one-stage and two-stage methods are limited.[1] They rest on small case series and few have reported relevant clinical outcomes, including functional patency, duration of CVC dependency, and postoperative complications. In addition, an insufficient number of studies have used intention-to-treat analysis to account for the risk of primary fistula failure. The majority of these studies have concentrated on the fistula-related outcomes rather than patient centric and patient-reported outcomes (PROs), including the quality of life (QOL) measure.[3] There is a clinical equipoise in the surgical approach for the creation of a BBAVF and it is unclear whether patients prefer a one-stage or two-stage procedure.[1] Currently, the decision to use one-stage or two-stage approach varies widely among access surgeons and is based on factors such as the size of basilic vein and surgeon's bias or preference. A patient-centered approach, incorporating a balance between population-based evidence and individual patient perspectives might be preferred. This pilot study will allow us to understand patient-centered outcomes and QOL measures regarding the respective BBAVF techniques. We will use the valuable results to design a Patient-Centered Outcomes Research Institute (PCORI)-sponsored pragmatic clinical trial to determine the optimal surgical procedure for a BBAVF and to understand the perspective of patients receiving a complex AVF.

The plan is to enroll 10 patients (n=5 in each group) with ESRD receiving hemodialysis with a CVC from the Banner University Medical Center. Within each cohort, the subjects will be randomized in a 1:1 ratio to one. Within each cohort, the subjects will be randomized in a 1:1 ratio to one stage and two-stage surgical approaches. The randomization scheme is as follow:

**Methods:**

The target population are patients on renal replacement therapy who are receiving hemodialysis (HD) with central venous catheters (CVCs) at the time of the surgery and are candidates for a new BBAVF. The surgery is a standard of care procedure that is being done whether the potential subject is enrolled in the study. Upon enrollment the study subject will fill out the PROMIS/CAT questionnaires. The study team will follow a randomized protocol so the study subject will be randomized to the one or two stage approach. The subjects will then be seen at the standard of care intervals for follow-up. At the 6 month and 12-month standard of care follow-up visits the subjects will be asked to fill out the PROMIS/CAT questionnaires again. The subjects medical record will be followed for AE and SAE study related problems during the 12 months post surgical procedure.

Primary endpoint is Primary Clinical Functional Patency, defined as the successful use of the index fistula with two dialysis needles for at least 75% of dialysis sessions within a 4-week period to achieve the prescribed dialysis. The primary endpoint will be compared between two techniques during available follow-up up to 12-months (from the index procedure in the one-stage approach and the first procedure for the two-stage approach). Secondary endpoints will include: 1) Fistula-related outcome: stenosis and thrombosis, wound infection, arm swelling, hand ischemia, and surgery or intervention; 2) CVC-related outcome: duration of catheter-dependency, infection, bacteremia, and additional CVC procedure (exchange, placement of new catheter); and 3) Composite outcomes of Primary Clinical Functional Patency or CVC-related bacteremia or death. We will compare the PROs using the Patient-Reported Outcome Measurement Information System (PROMIS) Computerized Adaptive Testing (CAT) in the randomized patients.

Hypothesis: Primary Clinical Functional Patency will be superior following two-stage approach compared with the one-stage BBAVF approach. Patients who underwent the two-stage procedure will have higher risks of infectious complications due to a more extended CVC dependency. The PROs will be affected by the number of procedures (one vs. two), postoperative fistula-related or CVC-related complications, and the duration of CVC dependency.

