**Statistical Analysis Plan:**

The primary analysis of the primary endpoint will be a comparison of the primary clinical functional patency by treatment approach, where the distributions are based on available follow up to 12 months. A log-rank test will be used to evaluate the null. The secondary analytic method of the secondary endpoints will utilize a Cox regression model to adjust for the subject factors to adjust for baseline imbalance such as vein size. Based on a recent publication utilizing primary patency rate as the main outcome, the reported rates of primary functional patency of one-stage BBAVF was 56% at 12-month follow-up and was 72% for the two-stage procedure.[12] Based on a two-sided Fisher's exact test at significance level of 5%, a sample size of 153 per group is required to achieve a power of 80% to detect the percentage patency difference of 16% (56% vs. 72%). A sample size of 336 participants (168 per arm), with an estimated loss to follow-up rate of 10%, will be required to achieve a 5% significance level. With the restraint of the time and resources of this ASDIN research grant, the pilot trial will be exploratory and will be used to demonstrate the feasibility of the research plan in a high-risk ESRD population and the recruitment target.

The changes in the individuals' PROMIS domain scores and overall scores from the baseline will be compared between the patients who underwent a one-stage procedure and those who had a two-stage procedure. The analysis will be performed after excluding those who do not complete the two-stage procedure (only first procedure for two-stage approach). The impact of clinical events including infection and catheter-related complication on PROMIS domain scores will be evaluated using the student T-test.

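### Follow-up PROMIS is tied to the 6- and 12-month clinic visits with no route for patients who miss them, so unequal, health-related loss can make one arm look better than it is

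*Combined protocol and SAP*

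**What the plan says.** Baseline collection covers everyone: "Upon enrollment the study subject will fill out the PROMIS/CAT questionnaires" (Methods). For follow-up, the same section says "At the 6 month and 12-month standard of care follow-up visits the subjects will be asked to fill out the PROMIS/CAT questionnaires again". The document describes no telephone, postal, remote or dialysis-unit collection, no visit window, no rule for a missed visit and no method for missing scores.

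The Statistical Analysis Plan makes change the analysis variable: "PROMIS domain scores and overall scores from the baseline will be compared between the patients who underwent a one-stage procedure" and those who had the two-stage procedure. It adds a restriction: "The analysis will be performed after excluding those who do not complete the two-stage procedure". The one-stage arm has no matching exclusion, although Methods says the patient-reported outcomes will be compared among those randomised.

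The plan expects serious events. One secondary endpoint is "Composite outcomes of Primary Clinical Functional Patency or CVC-related bacteremia or death", and the pilot is meant to show "the feasibility of the research plan in a high-risk ESRD population". The hypothesis paragraph in Methods predicts more infectious complications after the two-stage procedure because of longer catheter dependency. It also predicts that patient-reported outcomes will depend on postoperative complications and catheter duration. Nothing says how a death is handled in the PROMIS analysis.

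**The concern.** A patient who is in hospital or too ill to attend at month 6 or 12 has no score at that time under the plan as written, and a patient who has died cannot have one. The events that the plan expects to differ between the arms are also events that it expects to worsen PROMIS. If they keep patients from the clinic as well, the arm with more of them loses more of its poor scores, and its observed mean change improves for that reason alone.

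The pilot is intended to inform a larger pragmatic trial centred on patients' perspectives (Design). Whether PROMIS can be obtained from the sickest patients is therefore something the pilot should find out. As written, it need not report how many scores were missing, in which arm or why, and the same collection method could pass unexamined into the larger trial.

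**Working it through.** **The plan's own figure.** The only loss rate in the document is the 10% in the sample-size paragraph of the Statistical Analysis Plan. That calculation reproduces. For 56% vs 72%, two-sided 5% and 80% power, the continuity-corrected formula gives 153 per group, and exact enumeration of Fisher's test at 153 per group gives 80.3% power. The inflation to 168 per arm follows 153 × 1.1 = 168.3 (153 / 0.9 would give 170). The calculation concerns patency. No loss rate is stated for PROMIS or for the pilot, so using 10% below is an assumption.

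**Chance of any missing score in the pilot.** Inputs: 10 patients, 5 per arm (Design); loss rate d per patient, assumed independent.
- At least one of ten missing = 1 − (1 − d)^10.
- d = 5%: 1 − 0.95^10 = 40%.
- d = 10%: 1 − 0.90^10 = 65%.
- d = 20%: 1 − 0.80^10 = 89%.

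**Chance that the arms lose different numbers.** This is 1 − Σ P(k)², where P(k) is the binomial probability of k losses among 5. At 10% loss, P(0) to P(3) are 0.590, 0.328, 0.073 and 0.008, the squares sum to 0.462, and the result is 54%. At 5% it is 36%, and at 20% it is 68%.

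**Effect of one selective loss in an arm of five.** Assume change scores are normal and work in SD units, since the document gives no PROMIS SD. Simulating one million arms of five and dropping the lowest score, the remaining four average +0.29 SD, where all five would average 0. Dropping the lowest two gives +0.55 SD. For scale, the standard error of a difference between two arms of five is √(1/5 + 1/5) = 0.63 SD, so the single-loss shift is 0.29 / 0.63 = 0.46 of a standard error.

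**Effect in a larger trial with the same collection method.** Take two arms with identical true change. If the worst fraction d is lost, the mean of those remaining rises by φ(z_d) / (1 − d), where z_d is the normal quantile at d. This is 0.35 SD at 20% loss and 0.195 SD at 10%. If frailty, rather than the score itself, drives the loss, multiply by the correlation between the two. The spurious advantage of the arm with more loss is then:

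| Loss by arm | Lost patients are exactly the worst scorers | Correlation 0.5 | Correlation 0.3 |
|---|---|---|---|
| 20% vs 10% | 0.15 SD | 0.08 SD | 0.05 SD |
| 20% vs 0% | 0.35 SD | 0.17 SD | 0.10 SD |
| 10% vs 10% | 0 | 0 | 0 |

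The last row matters: equal and equally selective loss produces no bias. The loss rates and correlations are all assumptions.

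**The case against.** The strongest reply is that nothing here shows a bias. Bias needs loss that is related to health and also differs between the arms. The plan predicts more infections in the two-stage arm; it does not predict more deaths or missed visits, and it gives no completion rate. A reader might infer that the PROMIS contrast is biased toward the arm with more bad outcomes. The documents support only that it can be. That objection stands.

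Three further limits also stand.
- The 65% is the chance of any missing score, for any reason, in either arm. It is not the chance of a biased comparison, and its 10% is borrowed from the 336-patient calculation.
- A reader might infer that PROMIS exists only for patients who survive the study. That is too strong: a patient who dies after month 6 can still have a 6-month change score. That clinic visits are the sole route is likewise inferred from silence, and nothing forbids staff from contacting a patient who misses one.
- With five per arm, sampling error swamps a 0.29 SD shift, and no confirmatory PROMIS conclusion is planned.

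It is also fair to say that comparing scores among living patients is a recognised target, and that deaths are recorded elsewhere, through the composite and the 12-month record review. Ranking death as the worst outcome answers a different question, and with five per arm a single death could drive it.

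What the reply does not remove is the gap in collection. Staff following the plan as written have no instruction to obtain a score from a living patient who misses the visit. The exploratory label does not excuse this, because feasibility is one of the pilot's stated purposes.

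**Conclusion.** The concern holds as a conditional one, at minor severity. The plan gives up PROMIS scores that could be obtained, in a setting where its own hypotheses make health-related and unequal loss plausible, and it does not ask for the information that would show whether this happened. Some missing data in the pilot is likely: 65% for at least one of ten at an assumed 10% loss, 40% to 89% over 5% to 20%. One selective loss can move an arm of five by about 0.29 SD under normality. The size and direction of any actual bias cannot be established from the documents. The consequence falls mainly on the design of the larger trial, because a selection bias of this kind does not shrink as the sample grows.

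A second, explicit selection compounds the problem. The exclusion of two-stage patients who do not complete both stages can remove patients from one arm only. Better collection alone would not give an unselected comparison, because scores gathered from those patients would still be discarded.

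**What to change.** **Methods.** State that PROMIS will be sought from every living randomised patient at months 6 and 12, within a fixed window, whether or not the clinic visit takes place. Where the visit is missed, collect it remotely or at a dialysis session, and record the mode.

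**Statistical Analysis Plan.** Beside each PROMIS result, report deaths, completion and reasons for missing scores by randomised arm. Compare PROMIS by randomised arm, keeping the scores of two-stage patients who do not complete both stages, in line with the Methods statement that the comparison is among those randomised. A supportive ranking with death placed worst is optional, for the reasons given above.

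**Cost.** A few sentences of protocol text, a short table and a few extra contacts among at most ten patients. The drawback is a mixed mode of administration for a few of them, which is why the mode should be recorded. The document calls the instrument computerised but does not say that it can be completed remotely. That should be confirmed; the dialysis session is the alternative if it cannot.

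### AE and SAE recording is filtered on an undefined relatedness to the study, so harms outside the listed endpoints may go unrecorded

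*Combined protocol and SAP*

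**What the plan says.** All the relevant text is in the Methods section of the combined protocol and SAP. General safety follow-up is one sentence: "The subjects medical record will be followed for AE and SAE study related problems during the 12 months post surgical procedure". Earlier in that section the operation is described this way: "The surgery is a standard of care procedure that is being done whether the potential subject is enrolled in the study". What the study assigns is the approach: "The study team will follow a randomized protocol so the study subject will be randomized to the one or two stage approach". On visits it says: "The subjects will then be seen at the standard of care intervals for follow-up". No additional safety visits are described.

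The secondary endpoints are a separate route by which harms reach the data:

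- "Fistula-related outcome: stenosis and thrombosis, wound infection, arm swelling, hand ischemia, and surgery or intervention"
- "CVC-related outcome: duration of catheter-dependency, infection, bacteremia, and additional CVC procedure (exchange, placement of new catheter"
- "Composite outcomes of Primary Clinical Functional Patency or CVC-related bacteremia or death"

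None of these depends on relatedness.

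The available text does not define AE, SAE or relatedness to the study. It does not say who makes the judgement, or whether events are logged before attribution. The Statistical Analysis Plan section describes no tabulation of AEs or SAEs.

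**The concern.** In a randomized comparison of two surgical approaches, complications of the assigned approach belong in the comparison, whatever anyone thinks caused them. Here relatedness decides whether an event is recorded at all, when it should be something noted about a recorded event. The description of the surgery as standard care makes the filter harder to apply. A person abstracting records could reason in good faith that a complication of an operation the patient would have had anyway is not a study problem, and leave it out. Another could reason that the study chose the approach, so the complication counts. The same ten charts could then yield two different safety tables.

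At stake is how a short AE list from this pilot would be read. The Design section faults earlier comparisons partly because few reported outcomes such as postoperative complications, and the hypothesis in Methods names postoperative complications among the influences on patient-reported outcomes. A near-empty list could reflect few harms or a narrow reading of the rule, and nothing in the data would tell the two apart.

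**Working it through.** The plan states no figure for AE capture, so there is none to reproduce. The check is a reading of the text, followed by one illustration on assumed inputs.

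**Step 1: which route does each harm take?** The unlisted examples are mine; the documents do not name them.

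| Harm | Route into the data | Relatedness filter? |
|---|---|---|
| Stenosis, thrombosis, wound infection, arm swelling, hand ischemia | Fistula endpoint | No |
| Bleeding or other complication leading to surgery or intervention | Plausibly the fistula endpoint, through its surgery-or-intervention component | No |
| Catheter infection, bacteremia, catheter exchange or new catheter | CVC endpoint | No |
| Death | Composite endpoint | No |
| Nerve injury | AE/SAE sentence only | Yes |
| Bleeding without re-intervention | AE/SAE sentence only | Yes |
| Anesthetic or cardiopulmonary event | AE/SAE sentence only | Yes |
| Hospitalization without a listed intervention | AE/SAE sentence only | Yes |

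The gap is the last four rows and anything like them.

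**Step 2: does other text close the gap?** No. No other section requires all events to be recorded, and no definition ties relatedness to the assigned approach. The standard-of-care sentence leaves room for the narrow reading, and the randomization sentence leaves room for the broad one. On either reading, an unlisted harm enters only after a case-by-case judgement.

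**Step 3: what could under-capture do in a study of this size?** The Design section gives 10 patients, 5 per group. One event is 1/5 = 20 percentage points of an arm. That follows from the sample size for any outcome and is not evidence of loss.

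Let p be the true per-patient risk of an unlisted harm, q the share of cases judged related, and n the number of patients. With independent patients, the chance of recording at least one case is 1 − (1 − pq)^n. Neither p nor q is in the documents; both are assumed.

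| p | q | n = 10 | n = 5 (one arm) |
|---|---|---|---|
| 0.20 | 1 | 1 − 0.80^10 = 0.89 | 1 − 0.80^5 = 0.67 |
| 0.20 | 0.5 | 1 − 0.90^10 = 0.65 | 1 − 0.90^5 = 0.41 |
| 0.20 | 0.25 | 1 − 0.95^10 = 0.40 | 1 − 0.95^5 = 0.23 |
| 0.10 | 1 | 1 − 0.90^10 = 0.65 | 1 − 0.90^5 = 0.41 |
| 0.10 | 0.5 | 1 − 0.95^10 = 0.40 | 1 − 0.95^5 = 0.23 |
| 0.10 | 0.25 | 1 − 0.975^10 = 0.22 | 1 − 0.975^5 = 0.12 |

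Across these assumptions the filter can turn a harm that the pilot would probably see at least once into one that it would more likely miss.

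**The case against.** The strongest reply is that the term is merely undefined and has a natural broad reading. The study assigns the approach and the safety window is counted from surgery, so harms of the assigned operation are study related. On that view a one-line definition would be enough. This stands in part: the broad reading is available, so loss is not certain. But a definition alone would still leave each unlisted event to an individual judgement before it is recorded. Recording first and attributing afterwards removes that dependence at little extra cost.

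A second reply is that the endpoint list is already broad. That is right, and it limits the point to unlisted harms. The hypothesis that "Patients who underwent the two-stage procedure will have higher risks of infectious complications due to a more extended CVC dependency" adds nothing to the concern, because infection and bacteremia are endpoints collected without the filter.

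A third reply is that this is an exploratory feasibility pilot and that five patients per arm cannot give a reliable safety profile even with complete capture. That also stands. It limits the consequence but is no reason to keep an entry filter that costs little to remove.

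A reader might go further and infer that catheter events will be lost, that staff who know the technique will judge relatedness, that the unrecorded harms differ between arms, or that the follow-on trial will inherit a misleading safety profile. The documents do not support these. Catheter infection, bacteremia and procedures are listed endpoints. The text does not say who judges relatedness or what they know. It gives no evidence on which unlisted harms differ by arm, and it does not say that AE rates will inform the next trial's design.

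**Conclusion.** The concern holds in a bounded form. Harms that are not secondary endpoints reach the data only through a judgement of relatedness to the study. That term is undefined, and the plan's own description of the surgery as standard care allows such harms to be left out. Listed fistula and catheter outcomes, and death through the composite, are unaffected. So are the primary endpoint and the sample size.

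The size of any loss cannot be derived from the documents. The illustrative fall from 0.89 to 0.40 in the chance of recording any case among 10 patients rests on an assumed 20% risk and an assumed one-quarter share judged related. It should not be read as an estimate. The conclusion also rests on the available text; a definition on a removed page could narrow it. This is a change worth making, not a flaw that undermines the main comparison.

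**What to change.** Replace the safety sentence with a rule that, in both arms and over the follow-up window, the study records regardless of relatedness:

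- all SAEs, including hospitalizations and deaths;
- all AEs involving the access arm, either operation or its anesthesia, or the CVC.

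Record relatedness as a separate attribute of each event, say who assigns it, and tabulate all such events by assigned arm. In the same edit, state which operation starts the 12-month safety window in the two-stage arm. The primary endpoint clock is tied to the first procedure, but the safety sentence does not say which procedure it means.

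The cost is protocol wording and slightly more abstraction from records that are already being reviewed for 10 patients. The downside is that more background events of end-stage renal disease will be logged. The relatedness attribute and the by-arm table keep these interpretable.

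### The composite secondary endpoint joins a success (functional patency) to two harms (bacteremia, death) and has no stated direction, so its result cannot be read as good or bad

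*Combined protocol and SAP*

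**What the plan says.** The Methods section lists three groups of secondary endpoints. The third is "Composite outcomes of Primary Clinical Functional Patency or CVC-related bacteremia or death". Its first component is the primary endpoint, which the same section says is "defined as the successful use of the index fistula with two dialysis needles for at least 75% of dialysis sessions within a 4-week period", so it is a favourable event that a patient attains. The other two components are harms.

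The hypotheses in Methods give a direction for two of the ingredients: "Primary Clinical Functional Patency will be superior following two-stage approach compared with the one-stage BBAVF approach" and "Patients who underwent the two-stage procedure will have higher risks of infectious complications due to a more extended CVC dependency". They give none for the composite. For analysis, the SAP says only this: "The secondary analytic method of the secondary endpoints will utilize a Cox regression model", with adjustment for baseline factors such as vein size. It does not say what counts as the composite's event. Neither the protocol nor the SAP describes the patency component as loss or failure, ranks the components, or says which way the composite should be read.

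**The concern.** A composite can be interpreted only if its components point the same way. Here they do not. Read as a success measure, the composite credits an arm for bacteremia and death. Read as a failure measure, it penalises an arm for working fistulas.

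The plan's own expectations make this more than a matter of wording. The Design section describes a trade-off in which "two separate operations usually leads to more extended CVC dependency and a higher risk of CVC-related bacteremia", while the patency hypothesis favours the two-stage approach. This composite is the only listed endpoint that combines the two sides. As written, the expected benefit and the expected harm of the two-stage approach add together instead of offsetting each other. Death has a further problem: it appears only inside this composite and is not listed as an endpoint of its own.

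**Working it through.** **The plan's own figure.** No figure is given for the composite. The SAP's sample size is for patency, 56% versus 72%, two-sided 5%, 80% power. It reproduces: the continuity-corrected formula gives 153 per group, and exact Fisher power at 153 per group is 80.3%. The stated 168 per arm is 153 × 1.1 = 168.3. None of this depends on how the composite is defined.

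**Inputs for the illustration.**
- Patency *p*: 0.56 one-stage and 0.72 two-stage, from the SAP, taken here as the proportion attaining patency by 12 months.
- Harm *h* (bacteremia or death by 12 months): the documents give no rate. Assumed 0.05 one-stage and 0.05 to 0.20 two-stage.
- Harm independent of patency: assumed, and relaxed below.

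**Formulas.** As written (patency or harm): 1 − (1 − *p*)(1 − *h*). Aligned as failure (no patency, or harm): 1 − *p*(1 − *h*).

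| Arm | *p* | *h* | As written | Aligned failure |
|---|---|---|---|---|
| One-stage | 0.56 | 0.05 | 1 − 0.44 × 0.95 = 58.2% | 1 − 0.56 × 0.95 = 46.8% |
| Two-stage | 0.72 | 0.05 | 1 − 0.28 × 0.95 = 73.4% | 1 − 0.72 × 0.95 = 31.6% |
| Two-stage | 0.72 | 0.20 | 1 − 0.28 × 0.80 = 77.6% | 1 − 0.72 × 0.80 = 42.4% |

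When two-stage harm rises from 5% to 20%, the gap as written widens from 73.4 − 58.2 = 15.2 points to 77.6 − 58.2 = 19.4 points. The aligned two-stage advantage shrinks from 46.8 − 31.6 = 15.2 points to 46.8 − 42.4 = 4.4 points. The same added harm moves the two versions in opposite directions.

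**Without independence.** The Design section ties bacteremia to longer catheter dependency, so independence is doubtful. At 20% two-stage harm and 5% one-stage harm, with the same dependence in both arms:
- All harm in patients who attain patency: aligned failure is 0.44 + 0.05 = 49% versus 0.28 + 0.20 = 48%, an advantage of 1 point. As written it is 56% versus 72%, a gap of 16 points.
- All harm in patients who do not: aligned failure is 44% versus 28%, an advantage of 16 points. As written it is 0.56 + 0.05 = 61% versus 0.72 + 0.20 = 92%, a gap of 31 points.

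If dependence differs by arm, the aligned advantage can run from 44 − 48 = −4 to 49 − 28 = +21 points.

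**Why no hazard ratio is quoted.** Its size depends on when patency is attained, and the documents give no such times. Methods runs follow-up "from the index procedure in the one-stage approach and the first procedure for the two-stage approach", and Design says "The advantage of the one-stage approach is a shorter time between access creation and the cannulation for HD". A hazard ratio for attainment therefore mixes speed with eventual success.

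**The case against.** The strongest reply is that failure or loss of patency was obviously meant and a word was dropped. That is plausible. The SAP's talk of a patency rate at 12 months and its log-rank test would also fit patency as a maintained state whose loss is the event. But the composite uses a term that the plan defines as attainment. Even the failure reading leaves a choice between never attaining patency and losing it once attained. These have different events and event times, and the choice should not be made after the data are seen.

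A second reply is that this is one secondary endpoint, with no hypothesis or power claim, in an exploratory pilot of five patients per arm. That stands and sets the severity. Patency and bacteremia are also listed separately and can be read alone.

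A third is that every harm rate above is assumed, and that the near-disappearance of the aligned advantage needs all harm to fall in patients who attain patency. That also stands. The figures show how the definition behaves and are not a forecast.

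A reader might infer that the defect undermines the pilot's main comparison. The documents do not support that, because the primary endpoint is defined without the composite. A reader might also infer that the faulty definition will pass into the later trial. Design says the results will inform that trial's design, but not that this endpoint will be reused.

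**Conclusion.** The point holds as a minor one: the endpoint is wrong as written. That conclusion rests on the definition alone and needs no assumed rate, since a success and two harms are joined by "or" without a direction. The size is illustrative only. It depends on reading 56% and 72% as attainment by 12 months and on assumed harm rates.

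A reader might go further and conclude that the Cox model cannot serve this endpoint and must give way to a 12-month proportion. The documents do not require that. They plan to use whatever follow-up is available up to 12 months, so a simple proportion would create a short-follow-up problem that a time-to-event analysis handles by censoring.

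**What to change.** State what the event is and put every component in one direction. Since Methods defines patency as attainment, two wordings fit:

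- **Failure:** failure to achieve functional patency, or CVC-related bacteremia, or death, by 12 months.
- **Success:** functional patency achieved without prior bacteremia or death. This stays within the SAP's time-to-event framework, with bacteremia and death as competing events and shorter follow-up censored, so the Cox adjustment for factors such as vein size is kept.

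The two are exact complements only if harm after patency is treated the same way in both, so the definition should say how such harm counts. If the sponsor meant loss of patency, it should say so; a Cox model on time to the first failure event can then stay.

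Whichever is chosen, say which direction is favourable and report each component by arm, including death.

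The cost is one reworded endpoint and one added table row. Death is already a component, so no new type of data is needed. The drawback is that a competing-events analysis will be imprecise with 10 patients.
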